9.6 Safety Analyses

9.6.1 Extent of Study Treatment Exposure

Treatment duration will be summarized based on the Safety Analysis Set by treatment group. The following summaries will be included:

- Number of participants receiving at least 1 dose
- Number of participants receiving at least 1 dose of pre-treatment antihistamine
- Number of participants receiving at least 1 dose of pre-treatment corticosteroid
- Summary of number of doses administered
- Summary of total dose administered (mg)
- Summary of participants with an interrupted infusion
- Summary of weeks of exposure

A by-participant listing will be presented. Data on pre-treatment antihistamine and/or steroids will be listed.

9.6.2 Adverse Events

All TEAE summaries will be generated based on the Safety Analysis Set by treatment group and total. A summary of TEAEs will be generated and will include the number of events reported and the number and percentage of participants reporting:

- at least one AE
- anv severe AE
- any treatment-related AE
- any severe treatment-related AE
- any AE with outcome of death
- any SAE
- any treatment-related SAE
- any AE leading to the discontinuation of study treatment
- any treatment-related AE leading to discontinuation of study treatment
- any AE leading to discontinuation from the study
- any treatment-related AE leading to discontinuation from the study.

A summary of AEs will be presented by MedDRA SOC and PT. A breakdown of the number and percentage of participants reporting each TEAE, categorized by SOC, PT, and maximum severity, will be presented. Note that counting will be by participant not event and participants are only counted once within each SOC or PT. An additional summary of treatment-related TEAEs by SOC, PT, and maximum severity will be presented.

Summaries of severe TEAE, treatment-related TEAE, severe treatment-related TEAE, TEAE with outcome of death, serious TEAE, treatment-related serious TEAE, TEAE leading to study treatment discontinuation. treatment-related TEAE leading to study treatment discontinuation, TEAE leading to study discontinuation, and treatment-related TEAE leading to study discontinuation will also be provided, grouped by SOC and PT.

Page 24 of 30

Statistical Analysis Plan Version Date: 19-Feb-2019

The first row on every treatment-emergent AEs summary will be the number and percentage of participants reporting at least one TEAE. Subsequent rows will be presented in descending order of participant counts in total with the most common SOC first, followed within each SOC by the PTs in descending participant count order.

A by-participant listing of all AEs will be provided. Details such as clinical signs and symptoms will be listed for infusion related reactions.

9.6.4 Deaths and Serious Adverse Events

A summary of SAEs, categorized by SOC and PT and coded according to the MedDRA dictionary, will be presented by treatment group and total in the Safety Analysis Set. Note that counting will be by participant not event and participants are only counted once within each SOC or PT. All SAEs will be listed by participant. An additional summary of treatment-related SAEs will be presented by SOC and PT.

AEs with an outcome of death will be summarized by SOC and PT. All AEs with an outcome of death will be listed.

9.6.5 Laboratory Data

Based on the Safety Analysis Set, continuous laboratory results will be summarized using International System (SI) of units by visit, treatment group, and pooled BMS-986263. Categorical results such as those for urinalysis will be summarized by number and percentage of participants in each category. These summaries will be based on central laboratory results. Summaries will present both actual and change-from-baseline results for continuous values. Not all clinical lab values will be summarized. Refer to the TFL shells for the specific parameters that will be summarized. Baseline to maximum postbaseline shift tables during the treatment period will be presented for hematology, blood chemistry, metabolic panel, and Hba1c and these summaries will not be pooled by treatment group.

Elevated postbaseline values will be descriptively summarized by counts and percentages of participants ever experiencing specified elevated values per the TFL shells at any postbaseline time point for ALT, AST, Total Bilirubin, alpha-fetoprotein,

Laboratory values below the lower limit or above the upper limit of quantification will be set equal to the lower or upper limit, respectively, for summary tables. These actual values will be displayed in the listings.

In rare circumstances where the number of evaluable lumbar spine segments changes over time for bone mineral density results, only participants with the same number and same segments as their baseline assessment will be included in change from baseline summaries of lumbar spine values. In addition, only participants with at least 2 evaluable lumbar spine segments at baseline will be included in the summary of the baseline time point.

Where specified in the TFL shells, figures will be provided for mean change from baseline by timepoint by treatment group, with error bars for standard deviation of the mean change from baseline.

All laboratory data specified in the summary tables will be present in listings.

Statistical Analysis Plan Version Date: 19-Feb-2019

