Abbreviated physical assessment			X		X		X			X					Abbreviated examinations will include vital signs, weight, an abdominal exam, assessments of ascites and hepatic encephalopathy, and symptom-focused assessments.
12-lead electrocardiogr am														X	ECGs should be after the participant has been supine for at least 5 minutes.
Liver biopsy														X	See Section 8.6.1.1.
MRE							X							X	MRE to be performed ± 7 days of this day to allow sites scheduling flexibility. Participants must fast for 4 hours

Table 2 On-Treatment Procedural Outline IM025006: Part 1, Treatment Period (Day 4 through Day 85)

Procedure/Vi sit Day				12-	week,	Doub	le-Bli	ind, Tı	eatmo	ent Po	eriod				Notes
(± 3 days for all visits	D 4ª	D 8	D 15	D 22	D 29	D 36	D 43	D 46 ^a	D 50	D 57	D 64	D 71	D 78	D 85	
unless otherwise noted)		W 1	W 2	W 3	W 4	W 5	W 6		W 7	W 8	W 9	W 10	W 11	W 12	
															prior to MRE. See Section 8.6.1.2.
Laboratory Ass	essm	ents													
	essm	ents	X		X		X			X		X		X	Pre-infusion when on a dosing day See Section 8.6.2.7 and Table 11.
Laboratory Ass Hematology Chemistry	essm	ents X	X X	X	X	X	X		X	X	X	X	X	X	See Section 8.6.2.7 and Table 11. Pre-infusion when on a dosing day
Hematology	essm			X		X			X		X		X		See Section 8.6.2.7 and Table 11.
Hematology	essm			X		X			X		X		X		See Section 8.6.2.7 and Table 11. Pre-infusion when on a dosing day
	essm			X		X			X		X		X		See Section 8.6.2.7 and Table 11. Pre-infusion when on a dosing day

Table 2 On-Treatment Procedural Outline IM025006: Part 1, Treatment Period (Day 4 through Day 85)

Procedure/Vi sit Day				12-	week,	, Doub	le-Bl	ind, Tı	reatmo	ent Po	eriod				Notes
(± 3 days for all visits unless	D 4ª	D 8	D 15	D 22	D 29	D 36	D 43	D 46 ^a	D 50	D 57	D 64	D 71	D 78	D 85	
otherwise noted)		W 1	W 2	W 3	W 4	W 5	W 6		W 7	W 8	W 9	W 10	W 11	W 12	
HbA1C														X	See Section 8.6.2.7 and Table 11.
Urinalysis			X		X		X			X				X	See Section 8.6.2.7 and Table 11.
Serum AFP														X	See Section 8.6.2.7 and Table 11.
Urine Pregnancy		X	X	x	X	X	X		X	X	X	X	X		For WOCBP only. Urine pregnancy test must be completed to confirm participant is not pregnant prior to each infusion. See Section 8.6.2.1.5.

Table 2 On-Treatment Procedural Outline IM025006: Part 1, Treatment Period (Day 4 through Day 85)

Procedure/Vi sit Day				12-	-week,	, Doub	ole-Bl	ind, T	reatmo	ent Po	eriod				Notes
(± 3 days for all visits unless	D 4ª	D 8	D 15	D 22	D 29	D 36	D 43	D 46 ^a	D 50	D 57	D 64	D 71	D 78	D 85	

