 - b) Participants taking anti-obesity agents (eg, ORLISTAT®) within 4 weeks of the first dose of study treatment.
 - c) Participants receiving interferon therapy for any disease, or received interferon therapy for any disease within 52 weeks prior to administration of study treatment.
 - d) The participant takes any vitamin A containing supplements or multivitamins, or vitamin A containing medications after signing the ICF.
 - e) Participants taking anti-diabetic or anti-dyslipidemic medication receiving stable doses for less than 30 days prior to the first dose of study medication.
 - f) Participants unable to comply with restrictions and prohibited treatments.
 - g) Participants who have not discontinued other investigational agents must be discontinued at least 12 weeks or 5 half-lives before the first dose of study treatment, whichever is longer.
 - h) Prior exposure to BMS-986263
 - i) The participant has received recent treatment with alternative therapies, which, in the opinion of the investigator, could potentially confound clinical or laboratory assessments (eg, herbal supplements).
- 4. Physical and laboratory test findings
 - a) Evidence of organ dysfunction or any clinically significant deviation from normal in physical examination, vital signs, ECG, or clinical laboratory determinations beyond what is consistent with the target population
 - b) Body mass index (BMI) > 34 kg/m^2 . Participants with a BMI of $30\text{-}34 \text{ kg/m}^2$ must have an ALT \leq upper limit of the normal range (ULN).

- c) The participant's baseline laboratory test results include abnormal values considered to be clinically significant by the investigator.
- d) The participant's laboratory test results at screening include any of the following:
 - albumin < 3.5 g/dL
 - INR > ULN
 - ALT value $> 2 \times$ the ULN
 - hemoglobin A1c \geq 9.0%
 - total bilirubin > ULN
 - hemoglobin < lower limit of normal (LLN)
 - platelet count $< 100,000/\mu L$
 - white blood cell count $\leq 3000/\mu L$
- e) Glomerular filtration rate < 30 mL/min/1.73 m² according to the Modification of Diet in Renal Disease equation.
- f) The participant's vitamin A levels at screening are > ULN
- g) Alpha-fetoprotein (AFP; see Exclusion 1e, above):
 - i. AFP > 100 ng/mL (> 82.6 IU/mL) OR
 - ii. AFP ≥ 50 and ≤ 100 ng/mL (≥ 41.3 IU/mL and ≤ 82.6 IU/mL) with liver ultrasound showing findings suspicious for HCC.
- 5. Not applicable.
- 6. Allergies and adverse drug reaction

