8.6.2.1.6 Laboratory Test Result Abnormalities

The following laboratory test result abnormalities should be captured on the nonserious AE eCRF page or SAE Report Form electronic, as appropriate. Paper forms are only intended as a back-up option when the electronic system is not functioning.

- Any laboratory test result that is clinically significant or meets the definition of an SAE
- Any laboratory test result abnormality that required the participant to have study treatment discontinued or interrupted
- Any laboratory test result abnormality that required the participant to receive specific corrective therapy

It is expected that wherever possible, the clinical rather than laboratory term would be used by the reporting investigator (eg, anemia vs low hemoglobin value).

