9.3.2 Safety

Safety assessments will be performed using the safety population. For analysis, all treatment- emergent AEs recorded that occur during the conduct of the study will be listed and summarized by system organ class, preferred term, and treatment. Vital signs and clinical laboratory test results will be listed and summarized by treatment. ECG readings will be evaluated by the investigator and abnormalities, if present, will be summarized and listed.

Safety assessments include incidence of AEs, serious AEs,
AEs leading to discontinuation, and death, as well as marked abnormalities in clinical laboratory tests, vital sign measurements, ECGs, physical examinations 9.3.3 Other Analyses
· · · · · · · · · · · · · · · · · · ·

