The data collected during this study are confidential and proprietary to sponsor or designee. Any publications or abstracts arising from this study must adhere to the publication requirements set forth in the clinical trial agreement (CTA) governing study site or investigator participation in the study. These requirements include, but are not limited to, submitting proposed publications to sponsor or designee at the earliest practicable time prior to submission or presentation and otherwise within the time period set forth in the CTA.

APPENDIX 2 ADVERSE EVENTS AND SERIOUS ADVERSE EVENTS: DEFINITIONS AND PROCEDURES FOR RECORDING, EVALUATING, FOLLOW-UP AND REPORTING

ADVERSE EVENTS

Adverse Event Definition:

An adverse event (AE) is defined as any new untoward medical occurrence or worsening of a preexisting medical condition in a clinical investigation participant administered study drug and that does not necessarily have a causal relationship with this treatment.

An AE can therefore be any unfavorable and unintended sign (such as an abnormal laboratory finding), symptom, or disease temporally associated with the use of study drug, whether or not considered related to the study drug.

Events Meeting the AE Definition

- Any abnormal laboratory test results (hematology, clinical chemistry, or urinalysis) or results from other safety assessments (eg, ECG, radiological scans, vital signs measurements), including those that worsen from baseline, considered clinically significant in the medical and scientific judgement of the investigator. Note that abnormal lab tests or other safety assessments should only be reported as AEs if the final diagnosis is not available. Once the final diagnosis is known, the reported term should be updated to be the diagnosis.
- Exacerbation of a chronic or intermittent pre-existing condition including either an increase in frequency and/or intensity of the condition.
- New conditions detected or diagnosed after study intervention administration even though it may have been present before the start of the study.
- Signs, symptoms, or the clinical sequelae of a suspected drug-drug interaction.

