9.0 Statistical Methods

All analyses will use SAS® version 9.4 or higher

- Descriptive summaries will be tabulated by part, treatment group, and in total within part unless otherwise specified.
- Categorical data will be presented using counts and percentages, with the number of participants in each category as the denominator for percentages
 - For by-visit summaries denominators will be adjusted to reflect the number of participants in the study at the time of the visit
 - Percentages will be rounded to one decimal place except 0% and 100% which will be displayed without any decimal places and percentages will not be displayed for zero counts.
- Continuous data will be summarized using the number of observations (n), mean, standard deviation (SD), median, first quartile, third quartile, minimum, and maximum unless otherwise specified. Minimum and maximum will be rounded to the precision of the original value.
 - Mean, median, first and third quartiles will be rounded to 1 decimal place greater than the precision of the original value. The SD will be rounded to 2 decimal places greater than the precision of the original value, with the original value having up to a maximum of 3 decimal places.
- P-values will be presented to 3 decimal places where presented in the TFL shells
- Separate tables, figures, and listings will be presented for Part 1 and Part 2 of the study. Data will not be pooled across Parts 1 and 2.

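### Laboratory shift tables use the maximum post-baseline value, so falls in platelets, hemoglobin, white cells or albumin are hidden unless every treatment-period value is low

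*SAP*

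**What the plan says.** SAP section 9.6.5 plans this display: "Baseline to maximum postbaseline shift tables during the treatment period will be presented for hematology, blood chemistry, metabolic panel, and Hba1c". No direction is set by parameter, and no minimum or worst-value table is mentioned. SAP section 4.5.2 places platelets, hemoglobin and white cells in the hematology panel and albumin in the chemistry panel.

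The other participant-level count in section 9.6.5 concerns rises only: "Elevated postbaseline values will be descriptively summarized by counts and percentages of participants ever experiencing specified elevated values per the TFL shells". The legible parameters are ALT, AST, total bilirubin and alpha-fetoprotein, and the list then breaks off. The section refers to the TFL shells for which parameters are summarized, for the elevated thresholds and for some figures. It does not refer to them for the statistic that defines a shift.

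On the protocol side, section 8.4.2 excludes participants with "hemoglobin < lower limit of normal (LLN") and also those with low albumin, platelets or white cells. Protocol section 9.3.2 names "marked abnormalities in clinical laboratory tests, vital sign measurements, ECGs, physical examinations" among the safety assessments and does not restrict these to elevations.

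**The concern.** A shift table is read to see how many participants in each arm moved out of range. For a test where low is the concern, the maximum selects the most favourable value each participant had. One in-range result cancels any number of low ones. Participants with low hemoglobin are screened out, so a new fall is the change such a table should detect, and it is the change this rule suppresses.

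The suppression applies in every arm. A real difference between active drug and placebo in the number of participants whose counts fell could therefore show as zero against zero. No efficacy result is affected. What is at stake is a falsely reassuring safety table.

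**Working it through.** The documents state no figure to reproduce here; the check is one of counting.

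**Inputs**
- Shift statistic: maximum value in the treatment period (SAP 9.6.5).
- Part 1 hematology draws after baseline, from protocol section 1.2, Table 2: Days 15, 29, 43, 57, 71 and 85, so k = 6. The table is broken in extraction, but the columns can be read.
- Part 1 chemistry draws, same table: weekly from Day 8 to Day 85, so k = 12.
- Arm sizes: about 60 randomized 1:2:1, so 60 × 1/4 = 15, 60 × 2/4 = 30 and 60 × 1/4 = 15.
- Assumptions: categories are low, normal and high against the central-laboratory range, and all scheduled draws are available.

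**Step 1: when is the maximum low?** With low < normal < high, max(x₁,…,x_k) is low only if every xᵢ is low. A participant normal at baseline with 1 to k − 1 low values is not shown as low:
- hematology: 1 to 5 low values of 6 are hidden, and only 6 of 6 is shown;
- albumin: 1 to 11 low values of 12 are hidden, and only 12 of 12 is shown.

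**Step 2: patterns.** Scoring six hematology draws as low or normal gives 2⁶ = 64 patterns, of which 64 − 1 = 63 contain a low value. The minimum rule shows all 63 as normal-to-low. The maximum rule shows 1 and tabulates the other 62 as normal-to-normal. These are counts of patterns, not probabilities.

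**Step 3: a permanent fall.** If values turn low at draw j and stay low, all k values are low only when j = 1.
- Hematology: 1 of 6 possible onset draws is shown (low already on Day 15), and 5 of 6 are not.
- Albumin: 1 of 12 is shown (low already on Day 8), and 11 of 12 are not.

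**Step 4: two further effects of the rule.** If one value is above range and the rest are low, the participant is tabulated as normal-to-high; the low values are still hidden. If baseline is already low, a single in-range value gives low-to-normal, an apparent improvement. This can occur for platelets, because the screening cut-off is an absolute 100,000/µL and not the laboratory's lower limit.

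**Step 5: illustration only.** Take the 90 mg arm with about 30 participants, hemoglobin in range on Day 15 and below the limit from Day 29 through Day 85.

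| Participants affected | Minimum-based table | Planned table |
|---|---|---|
| 3 | 3/30 = 10% | 0/30 = 0% |
| 6 | 6/30 = 20% | 0/30 = 0% |
| 12 | 12/30 = 40% | 0/30 = 0% |

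The affected counts are invented to show the contrast; the documents give no expected rate.

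**The case against.** The strongest reply is that the SAP does not define the shift categories. If the shells graded results by degree of abnormality, the maximum could mean the worst grade in either direction and the problem would disappear. The shells are not available, so this cannot be excluded. However, the visible SAP defines no laboratory grading, and where it means maximum severity it says so, for adverse events in section 9.6.2. A shell built on the minimum would depart from the SAP's stated rule. The same uncertainty covers which parameters appear, since the shells choose them.

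A second reply is that parts of the text are missing: the elevated-value list breaks off, and no section 9.6.3 is visible. The broken sentence concerns elevated values, so its lost end is unlikely to supply a count of low ones. The conclusion is limited to the visible text.

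A third reply is that other outputs show falls, and this is true. Continuous results are "summarized using the number of observations (n), mean, standard deviation (SD), median, first quartile, third quartile, minimum, and maximum" by visit, summarized values are listed, and the external DMC reviews safety. Quartiles and minima at separate visits, however, do not combine into a number of participants ever low. Adverse event capture covers "Any laboratory test result that is clinically significant or meets the definition of an SAE", and also abnormalities that led to interruption, discontinuation or corrective therapy (protocol 8.6.2.1.6). Appendix 2 ties reporting to results "considered clinically significant in the medical and scientific judgement of the investigator". An asymptomatic low value that prompts no action need not be counted.

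Finally, the visible laboratory discontinuation rules in protocol 8.4.6.1 concern rises, for which the maximum is suitable. That supports keeping the maximum for ALT, AST, bilirubin, INR and HbA1c; it does not make it informative for the four tests the protocol screens for low values.

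**Conclusion.** The concern holds: the rule as written is wrong for platelets, hemoglobin, white cells and albumin. Followed exactly, it shows a normal-to-low shift in Part 1 only when all 6 hematology or all 12 chemistry values are low. A lasting fall that begins after the first on-treatment draw is hidden. This follows from the definition of a maximum and needs no assumed event rate. It rests on the usual low/normal/high categories and on complete draws; with missed draws the rule applies to the values that remain.

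The harm is limited. The underlying values stay in the summaries and listings, Part 1 is designed for estimation, and no efficacy result changes. What is missing is a systematic per-arm count of participants who fell below a lower limit, which the protocol's direction-neutral laboratory endpoint would lead a reader to expect. This should be corrected, but it does not threaten the trial's main conclusions.

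**What to change.** In SAP 9.6.5, define each shift by the worst post-baseline value in the direction of concern and name that direction for each parameter. Alternatively, keep the maximum table and add a sentence such as:

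*For platelets, hemoglobin, white blood cell count and albumin, shifts will also be tabulated by treatment group from baseline to the lowest value in the treatment period, with the number and percentage of participants having any post-baseline value under the central laboratory's lower limit.*

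It would also help to state the shift categories in the SAP, so that the rule does not depend on the shells.

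The cost is one or two sentences, matching shells and a few more tables from central-laboratory data already collected. The output becomes slightly longer. A minimum-based table also picks up isolated low values, but it does so in every arm, and placebo gives the reference. No visit, dose or clinical rule changes.
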